Primary Endpoint(s)	The primary endpoint is the -fold increase in antibody titer (using the Roche Elecsys® anti-SARS-CoV-2 S assay) from before receiving the study dose of vaccine to 30 days after the study dose.
Safety, Secondary, and Exploratory Endpoint(s)	
Secondary Safety Endpoints:
 
 Local and systemic vaccine reactogenicity and/or allergy Serious adverse events occurring during the 30 days following the additional dose of vaccine Treated acute cell-mediated and/or antibody-mediated allograft rejection (clinical or biopsy-proven) within 60 days following the additional dose of vaccine Development of de novo donor-specific anti-HLA antibody within 90 days of the vaccine Graft loss within 60 days of the vaccine Death within 60 days of the vaccine 
Secondary Efficacy Endpoints:
 
 Duration of anti-SARS-CoV-2 S antibody titers and neutralizing capacity in the year following the additional dose of vaccine

	
SARS-CoV-2 PCR positivity
 
Symptomatic COVID-19
 
COVID-19 requiring hospitalization
 
Log SARS-CoV-2 antibody titer at 30 days post-vaccine
 
Longitudinal changes in log SARS-CoV-2 antibody titer during the study
 
Exploratory Mechanistic Endpoints:
 
Anti-S1 and anti-RBD serology
 
Detection of SARS-CoV-2 spike protein in blood after the additional dose of vaccine
 
Additional serological panels and correlates of neutralizing antibody
 
SARS-CoV-2 virology, diagnostics, and sequencing, including novel variants of concern
 
Oral fluid anti-N and anti-S immunoglobulin levels (IgA (total and secretory), IgM, IgG)
 
Antigen-specific B cell response
 
Antigen-specific T cell response
 
Evidence of immune activation, transcriptomics and cytokine signaling
 
Durability of de novo donor-specific anti-HLA antibody

Accrual Objective	400 transplant kidney and liver transplant recipients with negative or low (≤ 2500 U/mL) antibody titers using the Roche Elecsys® anti-SARS-CoV-2 S assay after an authorized or licensed mRNA based anti-COVID-19 vaccination regimen.
Study Duration	
Accrual: 4 months
 
Screening, Vaccination and Follow-up: 13 months
 
Total Duration: 17 months

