3.3 Secondary Endpoints

3.3.1 Secondary Safety Endpoints

Local and systemic vaccine reactogenicity and/or allergy
Serious adverse events occurring during the 30 days following the additional dose of vaccine
Treated acute cell-mediated and/or antibody-mediated allograft rejection (clinical or biopsy-proven) within 60 days following the additional dose of vaccine
Development of de novo donor-specific anti-HLA antibody within 90 days of the vaccine
Graft loss within 60 days of the vaccine
Death within 60 days of the vaccine

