6.7 Immunosuppression Reduction

6.7.1 Immunosuppression (IS) Reduction

Participants on a tacrolimus-based regimen that includes MMF (or equivalent), with or without corticosteroid:

MMF (or equivalent) will be withheld for five days prior to and 2 weeks following vaccine administration. During the interval that MMF is withheld, no adjustments will be made to the CNI or corticosteroid dose.

Participants on a tacrolimus based regimen with a trough level ≥ 5 ng/mL, with or without ≤ 5 mg Prednisone (or equivalent) and no MMF or other antimetabolite

Reduce CNI by 25% of starting dose for 5 days prior to and 2 weeks following vaccine administration.

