11.5 Study Pausing Rules

If the following occur, relevant study interventions will be temporarily halted pending a DSMB review and recommendation as to whether the study may proceed.

1. Any Grade 4 or 5 event that is definitely or possibly attributed to the study dose of vaccine or to immunosuppression reduction.
2. Any probable or confirmed case of either acute myocarditis or acute pericarditis that occurs within 6 weeks of the study vaccine.
3. **Excess incidence of acute rejection (clinically treated or biopsy-proven):** Based on registry data, approximately 5-6 rejection events would be expected over the course of the study, independent of any effect of the study interventions. A pausing rule has been constructed such that the study would be paused if there is a >50% chance that the observed event rate exceeds three times the expected rate. The pausing rule will be applied to the study by group: (1) COVID-19 vaccine dose alone (2) MMF withdrawal (3) CNI reduction. Event rates triggering a pause are shown below:

Number of participants	Number of events required to trigger a pause	Event rate required to trigger a pause
10	3	30%
20	3	15%
30	3	10%
40	4	10%
50	4	8%
75	4	5%
100	5	5%
150	6	4.0%

200	7	3.5%
250	8	3.2%
300	9	3.0%
350	10	2.9%
400	11	2.8%

4. **Excess incidence of graft loss:** Based on registry data, it is expected that there will be approximately 6-7 graft losses over the course of the study, independent of any effect of the study interventions. A pausing rule has been constructed such that the study would be paused if there is a >50% chance that the observed event rate exceeds three times the expected rate. The pausing rule will be applied to the study by group: (1) COVID-19 vaccine dose alone (2) MMF withdrawal (3) CNI reduction. Event rates triggering a pause are shown below:

Number of participants	Number of events required to trigger a pause	Event rate required to trigger a pause
10	3	30%
20	3	15%
30	3	10%
40	4	10%
50	4	8%
75	4	5%
100	5	5%
150	6	4.0%
200	7	3.5%
250	8	3.2%
300	9	3.0%
350	10	2.9%
400	11	2.8%

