5. **Excess Mortality:** Based on registry data, it is expected that there will be approximately 5 deaths over the course of the study, independent of any effect of the study interventions. A pausing rule has been constructed such that the study would be paused if there is a >50% chance that the observed event rate exceeds three times the expected rate AND is determined to be possibly, probably or definitely related to a study intervention. The pausing rule will be applied to the study overall and by group: (1) COVID-19 vaccine dose alone (2) MMF withdrawal (3) CNI reduction. Event rates triggering a pause are shown below:

Number of participants	Number of events required to trigger a pause	Event rate required to trigger a pause
10	3	30%
20	3	15%
30	3	10%
40	4	10%
50	4	8%
75	4	5%
100	5	5%
150	5	3.3%
200	6	3.0%
250	7	2.8%
300	8	2.7%
350	9	2.6%
400	10	2.5%

12. Safety Monitoring and Reporting

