12.7.2 DSMB Review

12.7.2.1 Planned DSMB Reviews

The Data and Safety Monitoring Board (DSMB) shall review safety data one month after all study participants have received study vaccine, unless a safety event requires earlier review. They will review the study again when the database is locked after the last patient's last visit. Interim DSMB reviews may occur at any time at the discretion of the medical monitor or the protocol chair. Data for the planned safety reviews will include, at a minimum, a listing of all reported AEs and SAEs.

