13.7 Sample Size Considerations

Comparison of the primary endpoint will use a two-sided ranksum test. There will be 400 patients, 200 per treatment group. Power calculations assume an α of 0.05. The power of the study will depend on the distribution of -fold changes in each group.

We ran simulations in which -fold changes are log-normally distributed, and computed power based on the ratio of -fold change between the two groups. For example, if the average -fold increase in one group is a twofold increase and in the other group, a threefold increase, the ratio of -fold change is $3/2$ or 1.5. (This does not mean that each individual in one group experienced a twofold increase; some individuals would experience a greater increase, and some a smaller increase.) In the simulation, with an N of 400, generally the study has 80% power to detect a difference of 20% (e.g. mean 2.5-fold increase in one group vs 3-fold increase in the other.)

14. Identification and Access to Source Data**14.1 Source Data**

Source documents and source data are the original documentation where subject information, visits consultations, examinations and other information are recorded. Documentation of source data is necessary for the reconstruction, evaluation and validation of clinical findings, observations, and other activities during a clinical trial.

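### The rejection pausing rule (11.5, rule 3) checks the control arm whole but the IS-reduction arm only in two parts; a pooled check would be a cheap addition

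*Combined protocol and SAP*

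**What the plan says.** Section 11.5 pauses for excess rejection when a table of event counts is met. On scope, rule 3 says: "The pausing rule will be applied to the study by group: (1) COVID-19 vaccine dose alone (2) MMF withdrawal (3) CNI reduction". The consequence of meeting a rule is that "relevant study interventions will be temporarily halted pending a DSMB review". Section 13.7 fixes the arms: "There will be 400 patients, 200 per treatment group". Group 1 is therefore one randomised arm in full, and groups 2 and 3 together make up the other.

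The mortality rule is worded more widely: "The pausing rule will be applied to the study overall and by group".

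No other section sets a rejection limit for the IS-reduction arm. Section 13.5.2 plans two interim looks, but at dnDSA only, and again separately for each reduction group. Under section 12.7.2.1 the DSMB "shall review safety data one month after all study participants have received study vaccine, unless a safety event requires earlier review". Regimen is not a randomisation stratum (section 13.3), so the numbers on MMF withdrawal and on CNI reduction are not fixed.

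**The concern.** Section 5.3 names rejection as a risk of any reduction in immunosuppression, so the IS-reduction arm is where an arm-level limit matters most. Two separate checks each allow events up to one below their own trigger, and the two allowances add. If an excess is spread over both reductions, each part can stay below its trigger while the arm as a whole reaches or passes the count that would pause a control arm of the same size.

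What is at stake is a delayed or missed DSMB review of the arm during the "Accrual: 4 months" planned in the synopsis, when a pause could still spare new participants. The scheduled DSMB review comes after everyone has been vaccinated.

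**Working it through.** **Inputs.** Printed triggers (11.5, rule 3): 3 events at 10, 20 and 30 participants; 4 at 40, 50 and 75; 5 at 100; 6 at 150; 7 at 200. Expected rejections: 5-6 over the study. Arm size: 200 (13.7). The MMF/CNI splits below are assumptions.

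**The plan's own figures.** The printed rates equal events divided by participants (5/100 = 5%, 7/200 = 3.5%). The counts could not be rebuilt from 5-6 expected events per 400 and the >50% criterion: at 5.5/400, weak priors give 16-19 events at 400, against 11 printed. The check below therefore uses the printed triggers as they stand.

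**Step 1: most events without a pause.** This is (trigger of part A - 1) + (trigger of part B - 1), compared with the trigger at the pooled size.

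| MMF + CNI (either order) | Most without a pause | Trigger at pooled size |
|---|---|---|
| 20+20 | 2+2 = 4 | 4 |
| 50+50 | 3+3 = 6 | 5 |
| 75+75 | 3+3 = 6 | 6 |
| 100+50 | 4+3 = 7 | 6 |
| 100+100 | 4+4 = 8 | 7 |
| 150+50 | 5+3 = 8 | 7 |

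Between rows the reading matters. At 120+80 the lower rows (100 and 75) allow 4+3 = 7, equal to the trigger. The next higher rows (150 and 100) allow 5+4 = 9 against 7.

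**Step 2: chance of a pause, one look at 200, all risk already elapsed.** The true rate is three times expected: 3 x 5.5/400 = 4.125%. As written, P = 1 - P(A below its trigger) x P(B below its trigger), exact binomial. At 100+100, P(X ≤ 4 of 100) = 0.604, so P = 1 - 0.604² = 0.635. The pooled check adds the outcomes (3,4), (4,3) and (4,4): 2 x 0.191 x 0.199 + 0.199² = 0.1155, giving 0.751. For control, P(X ≥ 7 of 200) = 0.722.

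| Split (lower row) | As written | With pooled check |
|---|---|---|
| 100+100 | 63.5% | 75.1% |
| 150+50 | 65.0% | 74.7% |
| 160+40 | 67.9% | 75.3% |
| 110+90 | 74.5% | 78.5% |
| 120+80 | 74.2% | 78.2% |
| 140+60 | 76.2% | 79.3% |
| 170+30 | 74.3% | 77.2% |
| 190+10 | 80.1% | 80.6% |

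At the first three splits the IS-reduction arm pauses less often than control. At the others it already pauses more often. With the next higher row, the same formula at 120+80 gives 52.2% as written and 73.2% pooled.

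**Step 3: during accrual.** Assume steady 120-day accrual and risk falling evenly over 60 days after vaccine, the window of the secondary endpoint ("allograft rejection (clinical or biopsy-proven) within 60 days following the additional dose of vaccine"). The share of risk elapsed at day t (60 or later) is 1 - 60/(2t): 0.50 with 100 in the arm (day 60), 0.667 with 150 (day 90), 0.75 with 200 (day 120). Multiplying 4.125% by that share gives:

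- 50+50: 3.9% to 6.8%
- 100+50: 18.4% to 26.3% (control 23.3%)
- 75+75: 28.1% to 31.6% (control 23.3%)
- 100+100: 35.7% to 46.8% (control 42.4%)

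Simulating a check at every printed row through accrual gives 38-40% rising to 48-50%. If the risk is spread over 12 months instead, both figures are below 0.3%.

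**Step 4: false pauses at the background rate, 5.5/400 = 1.375%.** One look at 200: 2.5% to 3.5% at 100+100 and 2.3% to 3.1% at 150+50. Under continuous monitoring (simulation with a boundary fitted to the printed table, regimen share 50-90%): about 7% to 9-10%. The same simulation at 4.125% gives 75-80% rising to about 84%.

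**Step 5: the plan's >50% criterion at the pooled triggers.** Posterior probability that the rate exceeds 3.75-4.5%, under uniform and Jeffreys priors: 5 of 100, 62-82%; 6 of 150, 41-66%; 7 of 200, 26-52%.

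**The case against.** The separate checks are a sound choice. The arm holds two different interventions: for one regimen, "MMF (or equivalent) will be withheld for five days prior to and 2 weeks following vaccine administration"; for the other, the CNI dose is cut by 25%. A pause is meant to halt the relevant intervention, and the dnDSA looks are also split by reduction. An excess confined to one reduction is best caught by that group's own check. All of this stands, and it is why the group checks should stay. It does not argue against a further pooled trigger for DSMB review.

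Participants have other protection. Section 6.12 returns a person to baseline immunosuppression after a persistent creatinine or ALT rise, and section 8.3.3 requires weekly graft laboratory tests. Rule 1 pauses for an attributed Grade 4 or 5 event. The medical monitor receives monthly reports, and DSMB reviews may be called at discretion. A reader might infer that rejection in this arm is unmonitored; these provisions show that it is not. None of them, however, sets an arm-level rejection limit.

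A reader might also infer that the IS-reduction arm is always watched less closely than control. Step 2 does not support that: with the lower row, most splits tried already pause at least as often as control.

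Nor does the mortality rule show that a pooled check was forgotten. There, overall means the whole study, and no rule pools the two reductions.

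Finally, 7 of 200 usually falls short of the plan's own >50% criterion, and 8 of 200 is about borderline (38-66%). Eight events without a pause is therefore not a clear breach of that criterion. The plan does already apply the 7-of-200 row to control, and 5 of 100, which matters in mid-accrual, meets the criterion.

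**Conclusion.** The point holds as a modest, inexpensive improvement. Rule 3 gives the IS-reduction arm no rejection limit as a whole. On printed rows that arm can exceed the pooled trigger by one event at some splits, and only equals it at others.

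The size depends on a split and a between-row reading that the documents do not give. At a 4.1% true rate and one look at 200, the pooled check adds about 7-12 points at 100+100, 150+50 and 160+40. It adds 0.5-4 points at the other splits tried with the lower row, and more at some splits if the higher row is read. The gain also assumes an excess shared by both reductions and risk that comes early. With 200 in the arm enrolment is complete, so a pause then acts only on participants still within the 19-day reduction (5 + 14 days); the practical value lies in mid-accrual.

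**What to change.** Keep the three group checks and add one sentence to rule 3: *The table is also applied to the pooled IS-reduction arm (MMF withdrawal plus CNI reduction); if only the pooled limit is met, the DSMB decides whether one or both reductions are halted.*

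This needs no new data, table or committee. Its price is the extra chance of a false temporary pause shown in step 4, together with a 7-of-200 trigger that is usually stricter than the >50% criterion.

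The change is proposed for rule 3 only. Graft loss (rule 4) has the same scope wording, but the benefit there is small: rule 1 already pauses for an attributed Grade 4 or 5 event, and the kidney definition by dialysis needs more than 3 months. The 250-400 rows, which no listed group can reach, can be left alone.

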12.1 Overview

This section defines the types of safety data that will be collected under this protocol and outlines the procedures for appropriately collecting, grading, recording, and reporting those data. Adverse events that are classified as serious according to the definition of health authorities must be reported promptly (per Section 12.5, Reporting of Serious Adverse Events and Adverse Events) to the sponsor, DAIT/NIAID. Appropriate notifications will also be made to site principal investigators, Institutional Review Boards (IRBs), and health authorities.

Information in this section complies with ICH Guideline E2A: Clinical Safety Data Management: Definitions and Standards for Expedited Reporting, ICH Guideline E-6: Guideline for Good Clinical Practice, 21CFR Parts 312 and 320, and applies the standards set forth in the National Cancer Institute (NCI), Common Terminology Criteria for Adverse Events (CTCAE), Version [enter 5.0 or correct version applicable to trial] : <http://ctep.cancer.gov/reporting/ctc.html>.

12.2 Definitions

12.2.1 Adverse Event (AE)

Any untoward or unfavorable medical occurrence associated with the subject's participation in the research, whether or not considered related to the subject's participation in the research (modified from the definition of adverse events in the 1996 International Conference on Harmonization E-6 Guidelines for Good Clinical Practice) (from OHRP "Guidance on Reviewing and Reporting Unanticipated Problems Involving Risks to Subjects or Others and Adverse Events (1/15/07)" <http://www.hhs.gov/ohrp/policy/advevntguid.html#Q2>)

For this study, adverse events will be considered for association with the additional dose of COVID-19 vaccine and study mandated procedures as follows:

Vaccine Administration (Moderna COVID-19 Vaccine (monovalent, bivalent, and 2023-2024 formula as per protocol version), Pfizer-BioNTech COVID-19 Vaccine (monovalent, bivalent, and 2023-2024 formula as per protocol version)

All AEs occurring within 30 days following a single COVID-19 vaccine dose and SAEs up to 6 months post vaccine administration.

Study mandated procedures:

Any AE occurring within 24 hours of a protocol mandated blood draw
Any AE occurring within 24 hours of a protocol mandated nasal swab
Any AE occurring within 24 hours of an oral fluid collection
Any AE occurring during the period from the onset of immunosuppression reduction until 30 days after return to full immunosuppression and SAEs up to 6 months post return to full immunosuppression.

12.2.2 Solicited Adverse Events

For the purposes of this study, the following specific local and systemic reactogenicity events, as well as symptoms of a potential allergic reaction, will be solicited from the participant through a remote contact on Day 7 post-vaccination. Any other adverse events reported during the course of this remote contact will be reported on the AE eCRF. Study clinicians will follow all adverse events to resolution.

- Local reactions at the injection site including erythema/redness, swelling/induration (hardness), and pain.
- Systemic reactions including fever, myalgia, arthralgia, fatigue, headache, nausea, vomiting, diarrhea, and chills.
- Potential allergic reaction, which includes the following symptoms:
- Skin: hives, swelling other than injection site, itching, redness other than injection site, rash
- Respiratory: wheezing, shortness of breath, coughing, tightness in the throat or chest, sneezing, nasal stuffiness or congestion
- Gastrointestinal: trouble swallowing, abdominal cramps, diarrhea, nausea, vomiting
- Dizziness or lightheadedness

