8.3.2 Vaccination Visit: Day 0 (All Participants)

All participants will be scheduled for a vaccination visit.

Participants will have baseline research blood, oral fluid, and nasal samples collected on Day 0 per the Schedule of Events (Appendix 2 (COVID-19 Vaccine Dose Alone) and Appendix 3 (IS Reduction plus COVID-19 Vaccine Dose)). Following sample collection, the participant will proceed to the administration location and receive the assigned dose of COVID-19 vaccine (see [Section 6](#) for vaccine details).

Participants will be observed for 30 minutes post vaccine administration.

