12.3 Grading and Attribution of Adverse Events

12.3.1 Grading Criteria

The study site will grade the severity of adverse events experienced by the study subjects according to the criteria set forth in the National Cancer Institute’s Common Terminology Criteria for Adverse Events (CTCAE) Version 5.0. This document (referred to herein as the NCI-CTCAE manual) provides a common language to describe levels of severity, to analyze and interpret data, and to articulate the clinical significance of all adverse events. The NCI-CTCAE has been reviewed by the NIAID Medical Monitor and Protocol Chair and has been deemed appropriate for the subject population to be studied in this protocol.

Adverse events will be graded on a scale from 1 to 5 according to the following standards in the NCI-CTCAE manual:

Grade 1 = Mild; asymptomatic or mild symptoms; clinical or diagnostic observations only; intervention not indicated.

Grade 2 = Moderate; minimal, local or noninvasive intervention indicated; limiting age appropriate instrumental activities of daily living (ADL: Instrumental ADL refer to preparing meals, shopping for groceries or clothes, using the telephone, managing money, etc.)

Grade 3 = Severe or medically significant but not immediately life-threatening; hospitalization or prolongation of hospitalization indicated; disabling; limiting self-care activities of daily living (ADL: Self-care ADL refer to bathing, dressing and undressing, feeding self, using the toilet, taking medications, and not bedridden.)

Grade 4 = Life-threatening consequences; urgent intervention indicated.

Grade 5 = Death related to AE.

For grading an abnormal value or result of a clinical or laboratory evaluation (including, but not limited to, a radiograph, an ultrasound, an electrocardiogram etc.), a treatment-emergent adverse event is defined as an increase in grade from baseline or from the last post-baseline value that doesn't meet grading criteria. Changes in grade from screening to baseline will also be recorded as adverse events but are not treatment-emergent. If a specific event or result from a given clinical or laboratory evaluation is not included in the NCI-CTCAE manual, then an abnormal result would be considered an adverse event if changes in therapy or monitoring are implemented as a result of the event/result.

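### Solicited systemic and allergy-type symptoms are read once, at Day 7, with no pre-dose reading, so the reactogenicity rates can absorb background symptoms and a true arm difference can be diluted

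*Combined protocol and SAP*

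**What the plan says.** The first secondary safety endpoint in Section 3.3.1, repeated in Section 13.2, is "Local and systemic vaccine reactogenicity and/or allergy". Section 12.2.2 supplies the data: listed local, systemic and allergy-type items "will be solicited from the participant through a remote contact on Day 7 post-vaccination". Visit 8.7 windows allow one day either side of Week 1. The systemic list reads "Systemic reactions including fever, myalgia, arthralgia, fatigue, headache, nausea, vomiting, diarrhea, and chills", and the allergy list adds items such as cough, nasal congestion, itching and dizziness. Anything outside the lists goes elsewhere: "Any other adverse events reported during the course of this remote contact will be reported on the AE eCRF".

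For the vaccination visit, Section 8.3.2 says "Participants will have baseline research blood, oral fluid, and nasal samples collected on Day 0" and names no symptom checklist. None appears at screening (Section 8.2, Appendix 1), at Day -5 (Section 8.3.1) or in Appendices 2 and 3.

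The only increase-from-baseline rule, in Section 12.3.1, opens "For grading an abnormal value or result of a clinical or laboratory evaluation" and so does not reach reported symptoms.

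Day 7 lies inside the IS reduction period of Section 6.7.1. For participants on mycophenolate, "MMF (or equivalent) will be withheld for five days prior to and 2 weeks following vaccine administration". For those without it, "Reduce CNI by 25% of starting dose for 5 days prior to and 2 weeks following vaccine administration".

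Section 13.4.3 assigns a Fisher exact test to binary secondary endpoints, with no baseline adjustment.

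**The concern.** Fatigue, headache, joint or muscle pain, nausea and diarrhea can all be present without a vaccine. A single reading after the dose cannot show whether a symptom is new, worse or long-standing. Two things follow if the Day 7 answers are counted as they stand. The per-arm rates overstate how often the vaccine caused a reaction, and a real difference between arms is compressed, because participants who already have the symptom count as events whatever the vaccine did.

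The gap matters more than an unwritten derivation rule would. A rule can be added to the analysis plan later, but a baseline that was never collected cannot be recovered. The trial is open label (Sections 3.4 and 13.3), so asking participants or site staff afterwards what was new is not a neutral substitute.

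In the IS reduction arm, symptoms reported at Day 7 also arise under changed immunosuppression. One post-dose reading gives no means of saying how much belongs to the vaccine and how much to the reduction.

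**Working it through.** **Inputs from the documents.** 200 per arm (Section 13.7); Fisher exact test (Section 13.4.3), taken as two-sided at 0.05. The plan states no power for reactogenicity, so there is no figure of its own to reproduce; the 80% in Section 13.7 concerns the primary endpoint. The only reactogenicity rate given is 1-2% severe, from a cited cohort (Section 5.2).

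**Assumptions.** The endpoint is scored as any listed systemic symptom, yes or no, with no exclusion of pre-existing symptoms. Vaccine-caused risk *v* is 40% with vaccine alone and 55% with IS reduction. Background risk *b* is the same in both arms and independent of *v*.

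**Dilution.** Observed risk = 1 - (1 - v)(1 - b). The observed difference is therefore (1 - b) times the true difference. For b = 20%: 1 - 0.60 x 0.80 = 52%, 1 - 0.45 x 0.80 = 64%, difference 0.80 x 15 = 12 points.

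| Background b | Vaccine alone | IS reduction | Difference (points) | Exact Fisher power |
|---|---|---|---|---|
| 0% | 40.0% | 55.0% | 15.0 | 83% |
| 10% | 46.0% | 59.5% | 13.5 | 74% |
| 20% | 52.0% | 64.0% | 12.0 | 64% |
| 30% | 58.0% | 68.5% | 10.5 | 55% |
| 40% | 64.0% | 73.0% | 9.0 | 45% |

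Other assumed starting rates show the same pattern. For 30% v 45%, power falls from 85% at b = 0 to 64% at 20% and 42% at 40%. For 10% v 20%, it falls from 77% to 36% and 20%.

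**No false difference from equal background.** With v = 30% and b = 20% in both arms, both observed rates are 44% and the test rejects about 4% of the time.

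**If IS reduction itself changes symptoms.** Take v = 30% in both arms and b = 20% with vaccine alone, observed 44%. If b under reduction is 10%, the observed rate is 1 - 0.70 x 0.90 = 37%, 7 points lower. If it is 30%, the rate is 1 - 0.70 x 0.70 = 51%, 7 points higher. Fisher rejects about 26% of the time in either case. With b = 15% the shift is -3.5 points and rejection is about 9%. The documents do not say which direction applies, or whether there is any change.

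**What a Day 0 reading recovers.** Keep v = 40% v 55% and b = 20%, and treat the list as one symptom.

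- Best case: all background is present at Day 0 and every vaccine reaction raises the grade. The new-or-worsened counts are 40% v 55%, power 83%.
- Poor case: half the background (10%) is present at Day 0, half starts later, and no reaction raises an existing grade. The count is 0.90 - 0.80 x (1 - v), which gives 42% v 54%, still 12 points, power 64%.

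At 20% background, the reading therefore moves power from 64% to somewhere between about 64% and 83%.

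**The case against.** **Counting is inferred.** A reader might conclude that chronic symptoms are counted as vaccine reactions. The documents do not say so: they name the endpoint without giving its derivation. Section 12.2.1 considers association with the vaccine separately from the IS reduction period, and Section 12.3.2 has the site attribute each event on the AE/SAE form. This stands, and the point has to be conditional. The attribution step does not close the gap, though, because nothing links it to the reactogenicity endpoint.

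**The comparison is not biased.** A reader might also infer that the arm comparison is shifted. Randomisation balances chronic symptoms on average. Section 13.6 compares participants who do and do not undergo reduction, so symptom effects of the reduction belong to that contrast. They mislead only if the difference is read as a difference in vaccine reaction. Nor is the reduction always a withheld drug: one stratum has a tacrolimus dose reduction.

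**Other safety enquiry exists.** Medical history is reviewed at screening, events are assessed from Day 0 or Day -5, general health is asked about at follow-up visits, and unsolicited events are taken to 30 days. So asked once is true of the checklist only. But none of these grades the same items before the dose, and event collection starts before the dose only in the IS reduction arm (Section 12.4.1).

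**The rates are assumed and the remedy is partial.** Both are correct, and both are stated here as limits.

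**Conclusion.** The point holds in a limited form. The solicited systemic and allergy-type items have no pre-dose reading, and no rule isolates new or worsened symptoms. If Day 7 answers are tabulated as the endpoint, per-arm rates will include background symptoms and a true arm difference will be diluted by the factor (1 - b). Under the assumed 40% v 55%, backgrounds of 10% to 40% take Fisher power from 83% to between 74% and 45%. These sizes rest entirely on assumed rates.

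The documents do not support a claim of bias from chronic symptoms, or of a known direction for any effect of IS reduction. What can be said is that reduction effects cannot be separated from vaccine reactions. Injection-site items are little affected and the primary endpoint not at all. The change should be made, because it is cheap and the missing baseline cannot be reconstructed, but it concerns one secondary safety endpoint.

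**What to change.** - Give the same graded checklist at the Day 0 visit, before vaccination, in both arms.
- Keep the unadjusted Day 7 comparison as the effect of the randomised strategy.
- Report beside it the count of symptoms that are absent at the pre-dose reading, or at least one grade worse than it, with local and systemic items shown separately.
- State in the analysis plan how pre-existing symptoms are handled, and that Day 0 is already five days into IS reduction in that arm. It is a pre-vaccine baseline, not a pre-reduction one.

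**Cost.** One short form at a visit everyone attends, one eCRF page and some analysis-plan wording. Participants already vaccinated have no pre-dose reading, so the new-or-worsened count would cover only later participants. As earlier protocol versions used other vaccine formulations (Sections 6.1 to 6.4), it would also cover only later formulations. Recovery of power is partial, because symptoms that start after Day 0 are still counted, and a reaction in someone who already has the symptom counts only if it raises the grade.
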